Treatment comparisons of discrete efficacy variables will be made using a logistic regression analysis with treatment, baseline disease severity, and region in the model. The proportions and 95% confidence interval (CI) will be reported. If a patient needs to use rescue medication, the data after rescue onward will be considered missing and missing data will be imputed using the nonresponder imputation (NRI) method. All patients who discontinue the study or study treatment at any time for any reason will be defined as nonresponders for the NRI analysis for categorical variables after discontinuation onward. Additional analyses will be done using all observed data whether rescue medication was used or not.

Treatment comparisons of continuous efficacy and health outcome variables will be made using mixed-effects model of repeated measures (MMRM) with treatment, region, baseline severity, visit, and treatment-by-visit interaction as fixed categorical effects and baseline score and baseline score-by-visit interaction as fixed continuous effects. An unstructured covariance matrix will be used to model the within-patient variance-covariance errors. Type III sums of squares for the least squares means (LSMs) will be used for the statistical comparison and contrasts will be set up within the model to compare treatment groups at specific time points of interest.

Fisher exact test will be used for all adverse events (AEs), baseline, discontinuation, and other categorical safety data. Continuous vital signs and laboratory values will be analyzed by an analysis of covariance (ANCOVA) with treatment and baseline values in the model.

2. Schedule of Activities

Table JAIY.1. I4V-MC-JAIY Schedule of Activities

	Screening	Double-Blind, Placebo-Controlled							Post-treatment Follow-up
	Period 1	Period 2							Period 3
Visit Number	1	2	3	4	5	6	7	8	801 ^a
Weeks from Randomization		0	1	2	4	8	12	16 or ET	
Days from Randomization		0	7	14	28	56	84	112	
Visit Tolerance Interval (days)	-8 to -35		±2	±2	±2	±4	±4	±4	28 ± 4 after last dose
Procedure									
Inclusion and exclusion review	X	X							
Informed consent	X								
Clinical Assessments									
Demographics	X								
Medical history	X								
Substance Use (alcohol, tobacco use)	X								
Previous and current AD treatments	X								
Weight	X	X			X	X	X	X	X
Height		X							
Vital signs (BP and pulse rate)	X	X	X	X	X	X	X	X	X
Physical examination	X								
Symptom-directed physical examination ^b		X	X	X	X	X	X	X	X

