## 6.15. Safety Analyses

The general methods used to summarize safety data, including the definition of baseline and postbaseline are described in Section 6.2.

Safety analyses will include data from first dose of the study treatment to after rescue, unless otherwise stated, and patients will be analyzed according to the investigational product to which they were randomized at Visit 2. A sensitivity approach to the safety analyses will use data censored at last dose of the study drug for patients rescued to systemic therapy. These analyses will be conducted for treatment-emergent adverse events (TEAEs), serious adverse events (SAEs), AEs leading to permanent study drug discontinuation and special topics excluding deaths and malignancies. Additional analyses may be conducted using data after rescue to systemic therapy for some safety topics such as systemic TEAEs, and SAEs. Safety analyses will use the safety population defined in Section 6.2.1.

Safety topics that will be addressed include the following: AEs including TEAEs and SAEs, clinical laboratory evaluations, vital signs and physical characteristics, Columbia Suicide Severity Rating Scale (C-SSRS), the Self-Harm Supplement Form, safety in special groups and circumstances, including adverse events of special interest (AESI) (see Section 6.15.5), and investigational product interruptions.

Unless otherwise specified, by-visit summaries will include planned on-treatment visits. For tables that summarize events (such as AEs, categorical lab abnormalities, shift to maximum value), post-last dose follow-up data will be included. Follow-up data is defined as all data occurring up to 30 days (planned maximum follow-up time) after last dose of treatment including rescue, regardless of study period.

For selected safety assessments other than events, descriptive statistics may be presented for the last measure observed during post-treatment follow-up (up to 30 days after the last dose of treatment including rescue, regardless of study period).

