### 6.15.2. Adverse Events

Adverse events are recorded in the eCRFs. Each AE will be coded to system organ class (SOC) and preferred term (PT) using the Medical Dictionary for Regulatory Activities (MedDRA) version that is current at the time of database lock. Severity of AEs is recorded as mild, moderate, or severe.

A TEAE is defined as an event that either first occurred or worsened in severity after the first dose of study treatment and on or prior to the last visit date during the analysis period. The analysis period is defined as the treatment period plus up to 30 days off-drug follow-up time.

Adverse events are classified based upon the MedDRA PT. The MedDRA Lowest Level Term (LLT) will be used in defining which events are treatment-emergent. The maximum severity for each LLT during the baseline period up to first dose of the study medication will be used as baseline. If an event with missing severity is preexisting during the baseline period, and persists during the treatment period, then the baseline severity will be considered mild for determining treatment-emergence (that is, the event is treatment-emergent if the severity is coded moderate or severe postbaseline and not treatment-emergent if the severity is coded mild postbaseline). If an event occurring postbaseline has a missing severity rating, then the event is considered treatment-emergent unless the baseline rating is severe, in which case the event is not treatment-emergent. The day and time for events where onset is on the day of the first dose of study treatment will both be used to distinguish between pretreatment and posttreatment to derive treatment-emergence. Should there be insufficient data for AE start date to make this comparison (for example, the AE start year is the same as the treatment start year, but the AE start month and day are missing), the AE will be considered treatment-emergent.

In general, summaries will include the number of patients in the safety population (N), frequency of patients reporting the event (n), and relative frequency (that is, percentage;  $n/N*100$ ). For any events that are gender-specific based on the displayed PT, the denominator used to compute the percentage will only include patients from the appropriate gender.

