### **6.15.3. Clinical Laboratory Evaluation**

For the categorical laboratory analyses (shift and treatment emergent), the analysis period is defined as the treatment period plus up to 30 days off-drug follow-up time. The analysis period for the continuous laboratory analyses (e.g., change from baseline by time point) is defined as the treatment period excluding off-drug follow-up time.

All laboratory tests will be presented using the International System (SI) and US conventional (CN) units. The performing central laboratory reference ranges will be used to define the low and high limits. Results pertaining to the 4 key hepatic laboratory assessments (alanine aminotransferase [ALT], aspartate aminotransferase [AST], total bilirubin, and alkaline phosphatase [ALP]) will be included as a separate analysis to address the risk of liver injury as a special safety topic (see Section 6.15.5.1).

There is one special circumstance for laboratory values to be derived based on regularly scheduled, protocol-specified analytes. The low-density lipoprotein/high-density lipoprotein (LDL/HDL) ratio will be derived as the ratio of LDL cholesterol to HDL cholesterol. There are no central lab reference ranges for the LDL/HDL ratio.

The following will be conducted for the laboratory analytes collected quantitatively:

- **Box plots:** Values at each visit (starting from randomization) and change from last baseline to each visit and to last postbaseline measure will be displayed in box plots for patients who have both a baseline and at least 1 postbaseline visit. The last non-missing observation in the treatment period will be used as the last observation. Individual measurements outside of reference limits will also be displayed using distinct symbols overlaying the box plot. Original-scale data will be used for the display but for some analytes (for example, immunoglobulins) a logarithmic scale may be used to aid in viewing the measures of central tendency and dispersion. Unplanned measurements will

be excluded. Descriptive summary statistics will be included below the box plot along with p-values resulting from between treatment comparison in change from last baseline to last observation. An ANCOVA model with explanatory term for treatment and the baseline value as a covariate will be used. These box plots will be used to evaluate trends over time and to assess a potential impact of outliers on central tendency summaries.

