- **Treatment-emergent high/low analyses:** The number and percentage of patients with treatment-emergent high and low laboratory results at any time will be summarized by treatment group. Planned and unplanned measurements will be included. A treatment-emergent **high** result is defined as a change from a value less than or equal to the high limit at all baseline visits to a value greater than the high limit at any time during the treatment period. A treatment-emergent **low** result is defined as a change from a value greater than or equal to the low limit at all baseline visits to a value less than the low limit at any time during the treatment period. The Fisher's exact test will be used for the treatment comparisons. Number at risk (NAR) for the treatment-emergent high result is defined as the number of patients with a value less than or equal to the high limit at all baseline visits. NAR for the treatment-emergent low result is defined as the number of patients with a value greater than or equal to the low limit at all baseline visits for the treatment-emergent low result.

A listing of abnormal findings will be provided for laboratory analyte measurements, including qualitative measures. The listing will include but not limited to patient ID, treatment group, laboratory collection date, analyte name, and analyte finding. If needed by the safety physician/scientist, for analytes measured qualitatively, the number and percentage of patients with treatment-emergent abnormal laboratory results at any time will be summarized by treatment. Planned and unplanned measurements will be included. A treatment-emergent abnormal result is defined as a change from normal at all baseline visits to abnormal at any time postbaseline.

Note that additional analyses of certain laboratory analytes will be discussed within sub-sections of Section 6.15.5 pertaining to Special Safety topics (Section 6.15.5.1 for hepatic analytes, Section 6.15.5.2 for analytes related to hematological changes, Section 6.15.5.3 for analytes related to lipids, Section 6.15.5.4 for analytes related to renal function, and Section 6.15.5.5 for CPK).

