### 6.15.5.1. Abnormal Hepatic Tests

Analyses for abnormal hepatic tests will involve 4 laboratory analytes: ALT, AST, total bilirubin, and ALP. In addition to the analyses described in Section 6.15.3, this section describes specific analyses for this topic.

First, the number and percentage of patients with the following abnormal elevations in hepatic laboratory tests at any time will be summarized between treatment groups:

- The percentages of patients with an ALT measurement  $\geq 3\times$ ,  $5\times$ , and  $10\times$  the central laboratory upper limit of normal (ULN) during the treatment period will be summarized for all patients with a postbaseline value and for subsets based on various levels of baseline.
  - The analysis of  $3\times$  ULN will contain 4 subsets: patients whose non-missing maximum baseline value is  $\leq 1\times$  ULN, patients whose maximum baseline is  $>1\times$  ULN but  $<3\times$  ULN, patients whose maximum baseline value is  $\geq 3\times$  ULN, and patients whose baseline values are missing.
  - The analysis of  $5\times$  ULN will contain 5 subsets: patients whose non-missing maximum baseline value is  $\leq 1\times$  ULN, patients whose maximum baseline is  $>1\times$  ULN but  $<3\times$  ULN, patients whose maximum baseline is  $\geq 3\times$  ULN but  $<5\times$  ULN, patients whose maximum baseline value is  $\geq 5\times$  ULN, and patients whose baseline values are missing.
  - The analysis of  $10\times$  ULN will contain 6 subsets: patients whose non-missing maximum baseline value is  $\leq 1\times$  ULN, patients whose maximum baseline is  $>1\times$  ULN but  $<3\times$  ULN, patients whose maximum baseline is  $\geq 3\times$  ULN but  $<5\times$  ULN, patients whose maximum baseline is  $\geq 5\times$  ULN but  $<10\times$  ULN, patients whose maximum baseline value is  $\geq 10\times$  ULN, and patients whose baseline values are missing.
- The percentages of patients with an AST measurement  $\geq 3\times$ ,  $5\times$ , and  $10\times$  the central laboratory ULN during the treatment period will be summarized for all patients with a postbaseline value and for subsets based on various levels of baseline. Analyses will be constructed as described above for ALT.

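### SAP safety windows do not line up: event tables close at a 30-day planned maximum although Visit 801 may fall on day 32, and the laboratory sections differ on whether off-drug samples count

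*SAP*

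**What the plan says.** **Visit timing.** Protocol Section 2 (Table JAIY.1) schedules Visit 801 at "28 ± 4 after last dose". Adverse events, vital signs, chemistry, hematology, lipids and urinalysis are all marked for that visit.

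**General safety window.** SAP 6.15 includes data after the last dose in tables of events, and names categorical laboratory abnormalities and shifts to maximum among them. It then sets the limit: "Follow-up data is defined as all data occurring up to 30 days (planned maximum follow-up time) after last dose of treatment including rescue".

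**Adverse events.** SAP 6.15.2 repeats the limit: "The analysis period is defined as the treatment period plus up to 30 days off-drug follow-up time". It also requires a treatment-emergent event to occur "on or prior to the last visit date during the analysis period".

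**Laboratory data.** SAP 6.15.3 opens with the same window for both kinds of categorical analysis: "For the categorical laboratory analyses (shift and treatment emergent), the analysis period is defined as the treatment period plus up to 30 days", counted off drug. Further down, the quantitative high rule requires a change "to a value greater than the high limit at any time during the treatment period", and the low rule is parallel. For qualitative analytes the rule is wider: "A treatment-emergent abnormal result is defined as a change from normal at all baseline visits to abnormal at any time postbaseline". The hepatic percentages in 6.15.5.1 concern multiples of "the central laboratory upper limit of normal (ULN) during the treatment period will be summarized". The CTCAE and shift tables in 6.15.5.2, the lipid tables in 6.15.5.3 and the creatinine shift table in 6.15.5.4 are also tied to the treatment period. Only treatment-emergent creatinine in 6.15.5.4 uses the term analysis period. SAP 6.15.5.5 (CPK) says it follows the renal analyses but cites 6.15.5.2, which is hematology; renal is 6.15.5.4.

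**The concern.** There are two separate faults. First, the SAP justifies 30 days by calling it the longest planned follow-up, and the protocol's own visit tolerance runs beyond it. A patient seen on schedule on day 31 or 32 contributes safety data that the event tables do not admit.

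Second, the general laboratory rule and the analyte-specific rules give different answers for the same off-drug sample. A programmer who follows the opening of 6.15.3 includes a day-28 sample in the ALT or neutrophil tables. A programmer who follows 6.15.5.1 or 6.15.5.2 as written leaves it out. At stake is whether the by-arm counts of treatment-emergent events and laboratory abnormalities can be reproduced from the plan.

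**Working it through.** **1. The 30-day figure.** From the schedule, the earliest Visit 801 is 28 − 4 = day 24 and the latest is 28 + 4 = day 32. The SAP states a planned maximum of 30. Neither the nominal 28 days nor either end of the tolerance gives 30, so the figure is not reproduced. The shortfall is 32 − 30 = 2 days.

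Allowed days: 32 − 24 + 1 = 9. Inside the SAP limit: days 24 to 30, which is 7. Outside: days 31 and 32, which is 2, and 2/9 = 22% of the allowed days.

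The documents do not say how actual visit days are distributed. As an assumption, if they are uniform over the window, 22% of on-schedule visits fall on days 31–32. If they centre on day 28 with a normal spread limited to days 24–32, the share is about 0.6%, 10% or 16% for an SD of 1, 2 or 3 days.

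**2. The last-visit clause in 6.15.2.** Suppose the last dose is on the date of Visit 8, Visit 801 falls on day 31 or 32, and there is no unscheduled visit. Visit 801 then lies outside the analysis period, so the last visit inside it is Visit 8. Taken literally, events starting on days 1 to 30 after Visit 8 are not treatment-emergent, although 6.15 expressly admits them.

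**3. Laboratory rules side by side.** The last column shows where a Visit 801 sample taken on days 24–30 goes if each rule is read as worded.

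| SAP place | Analysis | Window as worded | Visit 801 sample |
|---|---|---|---|
| 6.15; 6.15.3 opening | Categorical, shift and treatment-emergent | Treatment period plus up to 30 days off drug | In |
| 6.15.3 | Quantitative high/low | Treatment period | Out |
| 6.15.3 | Qualitative analytes | Any time postbaseline | In |
| 6.15.5.1 | ALT, AST, bilirubin, ALP thresholds | Treatment period | Out |
| 6.15.5.1 | eDISH plot | Maximum postbaseline | In |
| 6.15.5.2 | CTCAE treatment-emergent and shift | Treatment period | Out |
| 6.15.5.2 | Thrombocytosis | Any postbaseline value | In |
| 6.15.5.3 | Lipid shift and treatment-emergent | Treatment period | Out |
| 6.15.5.4 | Creatinine shift | Treatment period | Out |
| 6.15.5.4 | Creatinine treatment-emergent | Analysis period | In |

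On days 31–32 the sample is also outside the 30-day rule, so only the three postbaseline rows, which carry no limit of their own, would admit it. SAP 5.1 runs the treatment period from Week 0 to Week 16, and Visit 801 follows it.

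**4. CPK.** If 6.15.5.5 means renal (6.15.5.4), treatment-emergent CPK uses the analysis period. If the cited 6.15.5.2 governs, it uses the treatment period.

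**5. Who is affected.** The Visit 801 points concern patients with a separate Visit 801. Patients entering Study JAHN do not need one (Protocol 5.1.3, figure footnote). Patients who stay in the study more than 28 days off drug may combine it with Visit 8 or early termination (Table JAIY.1, footnote a).

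**The case against.** The strongest reply is that this is loose drafting under a clear general rule. SAP 6.15 states 30 days outright, so programmers would not diverge on that number; only the label is wrong. The opening of 6.15.3 covers both shift and treatment-emergent analyses, and 6.15.5.4 uses both terms within one paragraph, which suggests careless wording and not deliberately different windows. Several of these sections also defer details to compound level safety standards, which are not in the documents and may settle the matter.

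Part of this stands. A declared 30-day cut-off would be legitimate, and the standards may resolve some of it. But 6.15.3 itself contrasts the treatment period plus 30 days with the treatment period excluding off-drug time, so the shorter term cannot safely be read as the longer one. The last-visit clause in 6.15.2 also remains open to the literal reading.

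A reader might infer more than the documents support:

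- **Two clocks for last dose.** SAP 6.15 refers to the last dose including rescue, but 6.15.1 defines that as the last date on study drug. There is no conflict.
- **Two ends of the treatment period, shifting weeks of data for patients who stop drug early.** SAP 6.15 counts from last dose regardless of study period, which largely answers this for event tables. What remains is a need for one defined term.
- **Conflicting safety populations.** Protocol 10.2 and SAP 6.2.1 agree, and the synopsis statement is qualified as holding unless otherwise specified.
- **All hepatic and hematology output confined to the treatment period.** The eDISH plot and thrombocytosis use postbaseline values.

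**Conclusion.** The plan is inconsistent as written, to a minor degree. The stated planned maximum is 2 days short of the protocol's schedule. The laboratory sections give different answers on off-drug samples for the quantitative high/low, hepatic threshold, hematology, lipid and creatinine shift tables. On the narrow reading these tables lose all Visit 801 samples, not only those from days 31–32. The CPK cross-reference is a plain error.

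The numbers of patients and events cannot be computed from the documents and are probably small. It would be wrong to infer that serious findings disappear. SAEs and deaths are listed (SAP 6.15.2.2), abnormal laboratory findings are listed (6.15.3), malignancies are summarised by arm whatever the gap since last dose (6.15.5.10), and the registry summary counts SAEs whether or not they are treatment-emergent (6.21). What is exposed is the reproducibility of the by-arm counts. The conclusion rests on the SAP text alone; the compound level safety standards could narrow it.

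**What to change.** - Define one safety analysis period in SAP 6.15, from first dose through Visit 801, at least 32 days after the last study-drug date as defined in 6.15.1. Alternatively, keep 30 days as a declared cut-off and delete the planned-maximum label.
- Use that single term for every treatment-emergent, threshold and shift analysis: the high/low rules in 6.15.3, the threshold percentages in 6.15.5.1, and the tables in 6.15.5.2, 6.15.5.3 and 6.15.5.4. The shift tables must be included, or the inconsistency stays.
- Reword the last-visit clause in 6.15.2 so that a Visit 801 on day 31 or 32 does not remove earlier follow-up events. This is needed under either option.
- Correct the cross-reference in 6.15.5.5 to 6.15.5.4.

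The cost is SAP wording in a few places, with no new data collection. The drawbacks are that a few late off-drug results would be counted under the randomised arm, and that the window may differ from the compound level safety standards, which should be checked first.

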### 6.15.1. Extent of Exposure

Duration of exposure (in days) will be calculated as follows:

- Duration of exposure to investigational product (including exposure after the initiation of rescue therapy): *date of last dose of study drug including rescue – date of first dose of study drug + 1.*

Last dose of study drug including rescue is calculated as last date on study drug. See the compound level safety standards for more details.

Total patient-years (PY) of exposure to study drug will be reported for each treatment group for overall duration of exposure. Descriptive statistics will be provided for patient-days of exposure and the frequency of patients falling into different exposure ranges in addition to cumulative exposures will be summarized.

Exposure ranges will be summarized as follows:

- $\geq 28$  days,  $\geq 56$  days,  $\geq 84$  days, and  $\geq 112$  days
- $> 0$  to  $< 28$  days,  $\geq 28$  days to  $< 56$  days,  $\geq 56$  days to  $< 84$  days,  $\geq 84$  days to  $< 112$  days, and  $\geq 112$  days

Overall exposure for a treatment group will be summarized in total PY which is calculated according to the following formula:

- $Exposure\ in\ PY\ (PYE) = \text{sum of duration of exposure in days (for all patients in treatment group)} / 365.25$

